6.3.3. Arm 4: Doxycycline

- Currently on Doxycycline (patients should have a washout period of at least 30 days from last dose if they have previously received this medication)
- Hypersensitivity to Doxycycline
- Participant, or investigator, objects to randomisation to Doxycycline
- Myasthenia Gravis
- Systemic Lupus Erythematosus
- Chronic Liver Disease
- Porphyria
- Alcohol dependence
- Suspected Syphilis

7. TRIAL PROCEDURES

7.1. Recruitment

Anonymised information on participants who are not randomised will be collected for CONSORT reporting and includes:

- age,
- gender,
- ethnicity,
- the reason not eligible for trial participation, or if they are eligible but declined.

7.1.1. Participant identification

Identification of potentially eligible trial participants by the research or clinical teams may make use of any or all of the following:

- From secondary care via contact with participants at specialist respiratory clinics or pulmonary rehabilitation classes. Clinic lists and rehabilitation class participant lists will be reviewed by a member of the clinical care team or research team, if delegated by the clinical care team, and medical records checked to identify suitable participants. Potential participants will then either be approached and given the brief Participant Information Sheet (bPIS) when they attend clinic or class or will be posted an invite letter and bPIS. Contact at clinic or class will be by a member of the clinical care team or local clinician. Postage of invitation letters and bPIS will be carried out by the clinical care team or a member of the trial team on delegation from the clinical care team.
- From local Bronchiectasis databases where participants have given prior consent to be contacted for future research projects, e.g. EMBARC registry, or local registers such as TAYBRIDGE, BRONCH-UK, or similar databases with appropriate approval in other NHS facilities as defined locally. Local Principal Investigator (PI) or delegated member of the clinical care or research teams will send out invite letters with bPIS to individuals who may be suitable to take part.
- Recruitment of participants registered via the Scottish Health Research Register (SHARE)
- From primary care via the Primary Care Networks. These participants will be sent an invitation letter and bPIS from the GP practice. GP practices will also be asked to display bPIS in their waiting rooms.

When first contact is via letter a bPIS will be sent which gives a general overview of the trial. Participants will be asked to contact the research team if they are interested in the trial. When first contact is in a hospital clinic they will be given a bPIS and will be asked to either return an expression of interest in a stamped addressed envelope or to contact a member of the research team by telephone or email; trial staff may also arrange a convenient time to call the participant. Contact details will be provided on the bPIS. Where a patient does not contact the research team the research team may contact them once via telephone, email or post to determine their interest in the trial.

Should individuals express an interest in taking part in the trial, the PI or delegate will contact the individual and ask for permission to check their medical notes. Individuals who returned a reply slip may have provided this permission on the slip in which case further contact with them would not be required prior to accessing their medical notes. Participants will receive a full Participant Information Sheet (PIS).

Recruitment may also utilise publicity materials including posters, information leaflets and advertisements.

The local PI will be responsible for recruitment but may delegate to other named individuals within the trial team.

7.1.2. Screening

At the screening visit (Visit 1) the procedures as detailed in the Schedule of Procedures, Appendix 4, will be carried out.

Assessment of eligibility will be carried out by the PI or other medically qualified delegate. Eligibility will be assessed at Visit 2, randomisation/baseline once all results have been reviewed.

Details of all participants consented to the trial and screened for eligibility will be recorded on the Enrolment and Randomisation Log, this will detail if a participant fails screening or goes on to be randomised.

Where an ineligible participant's medical condition, including ineligibility due to a recent infection, or concomitant medications change sufficiently so that they are deemed potentially eligible for the trial they may be rescreened one further time. All screening procedures will be repeated, including informed consent, and eligibility checked.

7.1.3. Ineligible participants

Where an individual is found to be ineligible for trial participation, they will be thanked and the reasons for the ineligibility fully explained. Any queries or questions will be answered by an appropriate member of the research team. If ineligibility is related to an incidental finding (IF) which is considered to be clinically significant, it will be reported to the participant's GP and/or consultant by the CI or Site PI, with the consent of the individual.

7.1.4. Payment

Participants will receive £100 per visit attended to cover travel expenses and recompense for attending research visits after each visit or at the end of their trial duration.

7.2. Consent

The PI retains overall responsibility for the recording of informed consent of participants at their site. They will ensure that any person delegated the informed consent process is duly authorised, trained and competent to participate according to the ethically approved protocol, principles of GCP and Declaration of Helsinki.

Where a participant requests to speak with a physician from the trial team the consent process will not be completed until the participant has spoken to the physician and had all their questions answered to their satisfaction.

For adults who lose capacity their previous wishes will remain legally binding, and this will remain valid unless the protocol changes significantly. If this occurs and further consent is required from a participant who has lost capacity, the participant's legal representative, or if not contactable, a professional legal representative will be asked for their consent.

In all cases the PI or delegate will consult with carers and take note of any signs of objection or distress from the participant – the participant will be withdrawn if they raise objection. Where appropriate, the participant will be withdrawn from any further clinical intervention and agreement will be sought from a carer to allow data collection.

7.2.1. Additional consent provisions for collection and use of participant data and biological specimens in ancillary studies, if applicable

Consent from participants will be gained for:

- use of their data in future research
- use of their specimens in future research
- use of their specimens in genetic research
- contact by trial staff for further ethically approved future research (optional)

Anonymised trial data will be kept under the control of the CI for future research use within the University of Dundee (UoD) and with other research collaborators (commercial and non-commercial).

Blood and sputum will be stored for future research in labs at the UoD. Specimens may be used for ethically approved research held within Tayside and will be registered with NHS Tayside Biorepository. Access for future use of those specimens will be via the CI. An EDTA blood sample for future genetic research will be obtained and patients will give consent for future genetic studies.

Any data collected to the point of withdrawal will be retained for reasons of public interest in the area of public health (Article 9(2)(i) General Data Protection Regulation (EU) 2016/679 GDPR).

7.3. Randomisation scheme

Participants will be randomised equally to any open arms they are eligible for. Participants will be allocated to an arm using a minimisation algorithm, with factors for centre, *Pseudomonas aeruginosa* infection recorded in the last 2 years and long-term use of macrolides.

Randomisation will initially open with a control arm and 3 treatment arms. When a treatment arm has recruited to its target, randomisation to that arm will be closed. When a new treatment arm is added, randomisation to that arm will be opened for all participants meeting the eligibility criteria for that arm.

Participants who have completed 56 days of follow-up (end of trial) may be rescreened and re-randomized if they are willing to participate in the trial again. Participants will receive a new copy of the current PIS, will be asked to complete a new Informed Consent Form, be given a new, unique participant identification number and eligibility will be rechecked prior to randomisation. All trial activities will be carried out as per protocol. Re-randomisation will be performed in the same way as for initial randomisations. Patients can be randomised a maximum of three times (i.e. initial randomisation and two re-randomisations).

7.3.1. Method of implementing the randomisation/allocation sequence

After successful completion of screening the participant will be assessed for eligibility for each treatment arm. This will be documented in the participant's medical notes and electronic Case Report Form (eCRF).

Participants will be randomised by the PI or delegate as per eligibility to the open trial arms.

The PI or delegate will use a centrally controlled web-based GCP compliant randomisation system, Tayside Randomisation System (TRuST), run by the UK Clinical Research Collaboration registered Tayside Clinical Trials Unit (TCTU). TRuST is provided by the Health Informatics Centre, UoD. TCTU use a validated randomisation program and will securely backup both the randomisation seed and the randomisation allocation.

The randomisation allocation will be emailed to the person completing the randomisation and Clinical Trials Pharmacy.

Access to be able to randomise a participant will only be given after completion of appropriate training.

7.4. Blinding

Nil, open label.

7.5. Emergency Unblinding

Not applicable

7.6. Baseline data

Baseline data will be collected at day 1 as per Schedule of Procedures, Appendix 4, and as described below, section 7.7.

7.7. Trial assessments

Trial assessments will be performed according to the Schedule of Procedures, Appendix 4. Where trial assessments identify any clinically significant incidental findings, these will be communicated to the participant's GP, with the participant's consent.

Trial assessments will be carried out according to trial specific guidelines.

Missed trial assessments or visits completed outside the visit window will not be reported as breaches where this is due to participant choice or a clinical decision, excursions will be documented, and trial statistician made of aware of discrepancies.

Medical history: focused medical history, taken from medical records and participant reporting, including the following information:

- History of chronic medical conditions related to inclusion and exclusion criteria
- Medication allergies

Review concomitant medications and therapies: taken from medical records and participant reporting at each visit.

Review of AEs: participants will be asked about the occurrence of any AEs since the previous visit, medical records will also be reviewed.

Severity of bronchiectasis: will be evaluated using the Bronchiectasis Severity Index and Medical Research Council dyspnoea score. Exacerbation assessment will use the EMBARC definition of exacerbation (Hill et al. 2017).

Physical examination: a detailed physical examination will be performed at screening to exclude participants with co-morbidities or other clinical disorders that would constitute an exclusion from the trial. This will include the following systems:

- Respiratory
- Cardiovascular
- Abdominal
- Neurological
- Dermatological

Height & weight: as per trial guidelines.

Vital signs: Blood Pressure, pulse, temperature, oxygen saturation as per trial guidelines.

Pregnancy test (urine): will be carried out for women of childbearing potential (WOCBP), as described in section 6.2. See also notes in the exclusion criteria section 6.2, regarding contraception.

Electrocardiogram (ECG): as per trial guidelines, will be reviewed by a doctor prior to randomisation.

6-minute walk test: this test assesses the distance (in metres) an individual can walk in 6 minutes. The participant walks back and forth along a marked walkway of 20 meters at their own pace.

Spirometry: post bronchodilator spirometry at visits will be carried using American Thoracic Society/European Respiratory Society's guidelines. Forced Expiratory Volume (FEV1) forced vital capacity (FVC) and Forced Expiratory Flow at 25-75% (FEF25-75) will be measured.

Questionnaires: as per schedule of procedures.

Blood samples: collected, processed, and stored as per laboratory manual. Full blood count, urea and electrolytes, liver function tests will be analysed by the local NHS laboratory. Samples will also be taken for trial outcomes. Additional blood samples will be collected for future biomarker and molecular microbiology research, dependent on participant consent, see section 7.2.1. A maximum of 100 ml of blood will be obtained at any visit.

Sputum sample: a sputum sample will be collected, processed, divided and stored as per laboratory manual. Participants will be asked to bring a spontaneous early morning sputum sample with them to visits from their second visit onwards. Where a participant is unable to produce a sputum sample at a visit a hierarchical approach to obtaining sputum samples will be used:

1. spontaneous sputum sample produced at the visit
2. spontaneous early morning sputum brought from home on the day
3. spontaneous early morning sputum brought in within the following 48 hours after the scheduled visit.
4. Induced sputum at sites able to perform induced sputum according to local protocols.

A sputum sample will be analysed locally for active neutrophilic inflammation at screening/baseline using NEATstik.

A sample will also be taken for trial outcomes. Additional sputum sample will be taken for future biomarker and molecular microbiology research, see section 7.2.1.

Nasal sample: brushing of the inferior turbinate will be performed to obtain nasal epithelial cells and the brush then placed into media for storage. Participants should not have a nasal brushing performed if they are receiving anticoagulants (Oral anticoagulants or warfarin) or have a history of deviated nasal septum, base of skull fracture or severe epistaxis. If any of these are present the nasal brushing will be omitted.

Safety assessments: participants will be requested to attend an unscheduled visit if they experience a bronchiectasis exacerbation or any other safety concern.

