6. PARTICIPANT ELIGIBILITY CRITERIA

6.1. Inclusion criteria

- ≥ 18 years.
- Able to provide informed consent.
- Capable of complying with all trial procedures and of completing the trial, in the opinion of the investigator.
- Bronchiectasis, confirmed by computed tomography (CT), showing bronchiectasis in 1 or more lobes.
- Normally produces sputum daily.
- Able to provide a sputum sample at the screening visit or between screening and randomisation^a.
- Active neutrophilic inflammation at screening/baseline indicated by a positive NEATstik (Neutrophil Elastase Airways Test) result^b.

^aRepeat sputum samples may be provided during the screening period, if the sample taken during the screening visit is deemed to be of insufficient quality or quantity by the laboratory.

^bA positive NEATstik test is equivalent to a NE concentration of 8 μ g/ml in sputum using the Proaxis active NE immunoassay. If NEATstik is not available for screening, a frozen sputum sample will be shipped to the central laboratory in Dundee where the immunoassay will be performed and used to confirm eligibility.

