10.3. Statistical analysis plan

The primary analysis will be performed on an intention-to-treat basis. Analysis of covariance (ANCOVA) will be used to compare the log₁₀-transformed NE between the control and each treatment arm after 28 days, with baseline log₁₀-transformed NE included as a covariate in addition to terms for trial arm, minimisation factors and relevant baseline prognostic variables. Missing data will be dealt with using multiple imputation, assuming missing-at-random is an appropriate assumption; methods exploring other mechanisms may be performed as appropriate. The estimated difference between the arms in log₁₀-transformed NE will be presented along with the corresponding 80% confidence interval and 1-sided p-value. Analysis makes a working independence assumption. To account for the re-randomisation of patients, cluster-robust standard errors will be computed (Kahan et al. 2021)

NE over the entire study period will be compared between arms using linear mixed effects models, including fixed effect terms for trial arm, stratification factors and relevant baseline prognostic variables, and a random intercept participant effect. Quality of life outcomes will be compared between arms using a similar approach.

Analysis of time to first exacerbation will be conducted using a Cox regression model incorporating trial arm, stratification factors and relevant baseline prognostic variables. The hazard ratio, 80% CI and 1-sided p-value associated with study arm will be obtained from this model, using cluster-robust standard errors. A Kaplan-Meier plot will be used to illustrate the relative time to first exacerbation in each arm and contemporaneous controls, with proportion of patients exacerbation-free after 28 and 56 days and associated 80% CIs provided.

Safety will be assessed by tabulating AEs that occurred in at least 10% of the safety population participants in either arm; these will be further broken down by severity. Treatment compliance (including number of expected doses taken/missed, number of dose

reductions (if applicable), reasons for missed doses/dose reductions, etc) will be summarised for each treatment arm.

Full details, including planned sensitivity analyses and the approach for handling missing data, will be provided in a separate Statistical Analysis Plan.

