16.4. Appendix 4 – Schedule of Procedures

	Visit 1 Screening	Visit 2 Baseline	Visit 3	Visit 4	Visit 5	Visit 6	Safety visit
	Days -35 to 0	Day 0	Day 7	Day 14	Day 28	Day 56	If required
Informed consent	X						
Eligibility check	X	X					
Demographics	X						
Medical history	X						
Concomitant medications	X	X	X	X	X	X	X
Physical examination	X						
Height & weight	X						
Record AEs		X	X	X	X	X	X
Record exacerbations		X	X	X	X	X	X
BP, pulse, temp, O ₂ stats	X	X	X	X	X	X	X
EKG	X						
6 minute walk test		X			X		
Post bronchodilation spirometry	X	X	X	X	X	X	X
QoL-B	X	X	X	X	X	X	
BIM baseline		X					
BIM follow-up			X	X	X	X	
BEST diary		X	X	X	X		
Full blood count, urea and electrolytes, liver function tests	X			X	X	X	X
Research blood sample for endpoint analyses		X	X	X	X	X	
Sputum sample for screening eligibility (NEATstik) ^a	X						
Research sputum sample for endpoint analyses		X	X	X	X	X	
Nasal sample		X			X		
Pregnancy test, if required	X	X	X	X	X		
Randomisation		X					
Dispensing of trial drugs		X					
Drug accountability					X		
Sub-study only							
Pulse wave velocity (PWV)		X			X	X	
Full-field Laser perfusion imaging (FLPI)		X			X	X	
Waist & Hip measurement		X					

^a If NEATSTIK is not available for screening, a frozen sputum sample will be shipped to the central laboratory in Dundee where the immunoassay will be performed and used to confirm eligibility.

Missed trial assessments or trial medication, or visits completed outside the visit window, will not be reported as breaches, where this is due to participant choice or a clinical decision.

Visits should be every as per schedule wherever possible. If a participant is unable to attend on the day of visit a delay of up to 2 days is accepted.

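### The 48-hour sputum fallback has no exception for Visit 2, so baseline NE, the covariate in the primary ANCOVA, can be collected after randomisation and after dosing has begun

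*Protocol*

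**What the plan says.** Protocol section 7.7 sets the collection rule: "Participants will be asked to bring a spontaneous early morning sputum sample with them to visits from their second visit onwards". It continues: "Where a participant is unable to produce a sputum sample at a visit a hierarchical approach to obtaining sputum samples will be used". The third option in that hierarchy is "spontaneous early morning sputum brought in within the following 48 hours after the scheduled visit". Neither the instruction nor the hierarchy exempts the second visit.

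In Appendix 4 the second visit is baseline, Day 0. The row "Research sputum sample for endpoint analyses" is first ticked there, and so are randomisation and "Dispensing of trial drugs". The schedule states no order among the three. The only sputum listed at Visit 1 is the eligibility sample.

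Section 6.1 asks that the participant be "Able to provide a sputum sample at the screening visit or between screening and randomisation". That criterion concerns eligibility; it does not secure the endpoint sample. Section 7.3.1 allows randomisation once screening has been completed successfully. Section 7.6 states: "Baseline data will be collected at day 1 as per Schedule of Procedures, Appendix 4", whereas section 3.1 and Appendix 4 call the same visit Day 0. No section states when the first dose is taken.

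Section 10.3 specifies the primary analysis as an ANCOVA of day-28 log10 NE, "with baseline log₁₀-transformed NE included as a covariate in addition to terms for trial arm".

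**The concern.** An ANCOVA covariate should be fixed before treatment can influence it. Under section 7.7 as worded, a participant with no sputum at Visit 2 may be randomised, receive the drug, start it, and then deliver the baseline sample within the next two days. In a drug arm that sample may already reflect treatment. In usual care it cannot.

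If the drug has begun to lower NE, adjusting for the lowered value removes part of the drug's own effect. Section 10.1 describes a screening design, so the consequence would be to make an active compound look weaker than it is. The same value also serves as day 0 for the secondary NE comparisons over time.

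**Working it through.** **Step 1: the plan's own figure.** Inputs from section 10.1: SD of log10 NE 0.5; target difference 0.25 log10 (standardised 0.5); one-sided 10% level; 42 per arm with up to 10% dropout; equal allocation; up to four covariates; R² from 0.1 to 0.4. Dropout leaves 42 × 0.9 = 37.8, taken as 37 evaluable per arm. I used two-group ANCOVA power with four random covariates: a noncentral t with 2 × 37 − 2 − 4 = 68 degrees of freedom, averaged over the distribution of the covariates. It gives 81.8%, 85.1%, 88.5% and 91.9% at R² = 0.1, 0.2, 0.3 and 0.4. This matches Table 10.1.1 exactly. The sample size is not in question.

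**Step 2: effect of late baselines.** Let

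- δ = 0.25, the true day-28 difference;
- f = share of drug-arm baselines collected after dosing began (assumed);
- g = share of the day-28 effect present when such a sample is produced (assumed);
- b = slope of day-28 on baseline log10 NE.

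ANCOVA estimates the day-28 difference minus b times the baseline difference. Late samples create an average baseline difference of f·g·δ in the direction of benefit, so

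estimate = δ − b·f·g·δ = δ(1 − b·f·g).

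I set b = √R², which is 0.316 at R² = 0.1 and 0.632 at R² = 0.4. This assumes equal SDs at the two times and that baseline NE carries all of the covariates' R². The second assumption puts b at the upper end for a given R².

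**Step 3: results (37 evaluable per arm).**

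| R² | f | g | Share of effect lost (b·f·g) | Estimate (log10) | Power |
|---|---|---|---|---|---|
| 0.1 | 0 | – | 0 | 0.250 | 81.8% |
| 0.1 | 5% | 25% | 0.4% | 0.249 | 81.6% |
| 0.1 | 10% | 50% | 1.6% | 0.246 | 80.9% |
| 0.1 | 20% | 100% | 6.3% | 0.234 | 77.9% |
| 0.1 | 30% | 100% | 9.5% | 0.226 | 75.8% |
| 0.4 | 0 | – | 0 | 0.250 | 91.9% |
| 0.4 | 5% | 25% | 0.8% | 0.248 | 91.6% |
| 0.4 | 10% | 50% | 3.2% | 0.242 | 90.6% |
| 0.4 | 20% | 100% | 12.6% | 0.218 | 85.6% |
| 0.4 | 30% | 100% | 19.0% | 0.203 | 81.4% |

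Example at R² = 0.4, f = 10%, g = 50%: 0.632 × 0.10 × 0.50 = 0.032, and 0.25 × (1 − 0.032) = 0.242. A simulation with 38 per arm gave the same estimates at R² = 0.4: 0.242 for this row and 0.203 for the last.

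**Step 4: type I error.** If the drug does nothing to NE, late samples have the same expected value as early ones. The baseline difference is then zero on average and the adjusted estimate is unbiased.

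**The case against.** The strongest reply is that the event should be rare and brief. Section 6.1 requires participants who normally produce sputum daily. Section 7.7 asks them to bring an early morning sample and ranks two same-day options ahead of the 48-hour one. The time of first dose is not stated, so a late sample is not necessarily an on-treatment one. Sites may collect sputum first as a matter of routine, and the laboratory manual, which is not at hand, may say so. All of this bears on size and stands. It does not remove the gap, because nothing in the protocol requires the endpoint sample to come first.

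A reader might infer more than the text supports, in four ways:

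- **Two to three days of dosing before baseline.** The allowance ends 48 hours after the visit, and a next-morning sample would follow less than a day of exposure.
- **A loss of 8-32% of the effect.** That figure takes b from 0.32 to 0.63 with g from 25% to 50%, and it describes affected participants only. Across an arm it must be multiplied by f.
- **A sample that never arrives leaves the analysis stranded.** Section 10.3 plans multiple imputation for missing data.
- **Knowing the allocation biases the sample.** The documents give no mechanism by which this would change a laboratory NE measurement.

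**Conclusion.** The point holds as a defect in a stated rule. Section 7.7 and Appendix 4, followed as written, permit a baseline NE obtained after randomisation and possibly after up to about 48 hours of drug, and section 10.3 then uses it as a covariate. The bias runs one way, toward no effect, for a drug that lowers NE early, and it does not create false positives for an inactive drug.

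The size is probably small. At 10% late and half the effect present, the loss is 1.6-3.2% of the target and about one point of power (81.8% to 80.9%, or 91.9% to 90.6%). Power falls to 75.8% or 81.4% only if 30% of drug-arm baselines are late and the whole day-28 effect is already present. Both f and g are assumptions with no source in the documents.

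The point still merits a change because it touches the primary covariate and prevention is nearly free. An analysis plan can set a post-dose baseline to missing, but it cannot recover a pre-dose sample that was never taken.

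**What to change.** In section 7.7 and in a footnote to Appendix 4, state that the Visit 2 research sputum must be obtained before randomisation and dispensing, and that the 48-hour option applies only to post-baseline visits. If no sample is produced, reschedule Visit 2 within the existing screening window. Record the times of the sample and the first dose, and treat any baseline sample found to be post-dose as missing under the planned imputation. Align the day 0 and day 1 labels for baseline at the same time.

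A stored aliquot of the screening sputum is not a good substitute. Appendix 4 schedules no endpoint sample at screening, and the specimen could be up to 35 days old.

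The cost is one sentence, one footnote, a check before randomisation and a few rescheduled Visit 2 appointments. Some of these could run up against the 35-day window, which section 6.2 extends only for a respiratory infection or exacerbation.
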